18. ANNEX 3. LIST OF MIGRAINE THERAPIES

Table 6 provides a list of other migraine therapies. Please note, combination products of products already listed are not included.

Table 6.List of Migraine Therapies

Drug class	Generic name
Triptans	Almotriptan
	Eletriptan
	Frovatriptan
	Naratriptan
	Rizatriptan
	Sumatriptan
	Zolmitriptan
Anticonvulsants	Carbamazepine
	Clonazepam
	Diazepam
	Gabapentin
	Levetiracetam
	Lorazepam
	Topiramate
	Valproic acid
Pain therapies	Buprenorphine
	Butorphanol
	Dezocine
	Fentanyl
	Hydromorphone
	Levomethadyl
	Levorphanol
	Meperidine
	Methadone
	Morphine
	Nalbuphine
	Opium tincture
	Oxymorphone

PFIZER CONFIDENTIAL

Drug class	Generic name
	Oxycodone
	Pentazocine
	Sufentanil
	Tapentadol
	Tramadol
	Aspirin
	Acetaminophen
	Butalbital
	Hydroxycodeine
	Codeine
	Dihydrocodeine
	Drocode
	Ibuprofen
	Magnesium
	Calcium
	Meprobamate
	Dipyridamole
	Diphenhydramine
	Chlorpheniramine
	Pseudoephedrine
	Phenacetin
	Phenyltoloxamine
	Phenobarbital
	Salicylamide
	Carisoprodol
	Ethoheptazine
	Methocarbamol
	Opium
	Orphenadrine
	Propoxyphene
Anti-depressants	Nefazodone
	Bupropion
	Amitriptyline

PFIZER CONFIDENTIAL

Drug class	Generic name
	Trazodone
	Nortriptyline
	Sertraline
	Fluoxetine
	Paroxetine
	Duloxetine
	Venlafaxine
Beta-blockers	Atenolol
	Bisoprolol
	Carvedilol
	Esmolol
	Labetalol
	Metoprolol
	Nadolol
	Pindolol
	Propranolol
	Sotalol
	Timolol
Anti-nauseants	Meclizine
	Ondansetron
	Granisetron
	Palonosetron
	Rolapitant
	Tolazamide
Antipsychotics	Risperidone
	Paliperidone
	Aripiprazole
	Quetiapine
	Haloperidol
	Olanzapine
Steroid	Corticosteroids
Antihistamines	Cyproheptadine
Botox	Botulinum toxin type A

PFIZER CONFIDENTIAL

Drug class	Generic name
	Botulinum toxin type B
Ergotamine	Dihydroergotamine
	Ergotamine
CGRP inhibitors (with the exception of rimegepant, exposure to these agents is criteria for exclusion)	Fremanezumab
	Erenumab
	Galcanezumab
	Ubrogepant
	Zavegepant
	Rimegepant
Ditans (exposure to these agents is criteria for exclusion)	Lasmiditan
Complementary medications	Butterbur (petasites)
	Feverfew (MIG-99)
	Caffeine

CGRP = calcitonin gene-related peptide

19. ANNEX 4. LIST OF KNOWN TERATOGENS

Table 7 provides a list of known teratogens. This list has been developed and will be continually updated based on the data available in the TERIS database of teratogenic agents and recent publications⁷²⁻⁷⁴.

Drug class/generic name	Half-life	Relevant exposure window ^a
Androgens		
Methyltestosterone	6 to 8 h	First, second, and third trimesters
Testosterone	Plasma half-life of testosterone ranges from 10 to 100 min. The cypionate and enanthate esters of testosterone have longer durations of action than testosterone. Cypionate half-life is about 8 d.	First, second, and third trimesters
Mesterolone	12 to 13 h	Not in TERIS. Assumed window: first, second, and third trimesters
Nandrolone	144 to 288 h	Unknown. Assumed window: first, second, and third trimesters
Oxandrolone	13.3 h	Unknown. Assumed window: first, second, and third trimesters
Prasterone	12 h	Unknown. Assumed window: first, second, and third trimesters
Fluoxymesterone	9.2 h	Unknown. Assumed window: first, second, and third trimesters
Angiotensin II receptor antagonists		
Candesartan	9 h	First, second, and third trimesters
Eprosartan	20 h	First, second, and third trimesters
Irbesartan	11 to 15 h	First, second, and third trimesters
Losartan	2 h	First, second, and third trimesters
Olmesartan	13 h	First, second, and third trimesters
Tasosartan	Not available, but half-life of angiotensin II receptor antagonists ranges from 1 to 3 d	First, second, and third trimesters
Telmisartan	24 h	First, second, and third trimesters
Valsartan	6 h	First, second, and third trimesters
Angiotensin-converting enzyme inhibitors		
Benazepril	10 to 11 h	First, second, and third trimesters

Table 7.	List of Known Teratogens	
----------	--------------------------	--

PFIZER CONFIDENTIAL

Drug class/generic name	Half-life	Relevant exposure window ^a
Captopril	2 h	First, second, and third trimesters
Cilazapril	9 h	First, second, and third trimesters
Enalapril	11 h	First, second, and third trimesters
Fosinopril	11.5 to 14 h	First, second, and third trimesters
Lisinopril	12 h	First, second, and third trimesters
Moexipril	12 h	First, second, and third trimesters
Perindopril	0.8 to 1 h	First, second, and third trimesters
Quinapril	3 h	First, second, and third trimesters
Ramipril	13 to 17 h	First, second, and third trimesters
Trandolapril	6 h	First, second, and third trimesters
Anti-arrhythmics		
Amiodarone	61 d	First, second, and third trimesters
Antibiotics		
Sulfamethoxazole/ Trimethoprim	8 to 10 h	3 months before conception and first trimester for MCMs and second trimester for preterm birth and low birth weight
Anticoagulants		
Acenocoumarol	8 to 11 h	First, second, and third trimesters
Dicumarol	1 to 2 d	At least 2 weeks before conception and first, second, and third trimesters
Phenprocoumon	4 to 6 d	First, second, and third trimesters
Warfarin	40 h	At least 2 weeks before conception and first, second, and third trimesters
Anti-epileptics		
Lamotrigine	Adult, 25.4 to 70.3 h (healthy volunteers); 12.6 to 58.8 h (epilepsy)	First, second, and third trimesters
Trimethadione/ Paramethadione	Paramethadione—12 to 24 h Trimethadione—11 to 16 h	First, second, and third trimesters
Valproic Acid, Valproate	9 to 16 h	Primarily first trimester, but MCMs have been associated with second and third trimester exposures
Carbamazepine	12 to 65 h	First, second, and third trimesters
Ethotoin	3 to 9 h	First, second, and third trimesters
Phenytoin, fosphenytoin	Phenytoin: 7 to 42 h Fosphenytoin: 15 min	First, second, and third trimesters
Primidone	10 h	First, second, and third trimesters

PFIZER CONFIDENTIAL

Drug class/generic name	Half-life	Relevant exposure window ^a
Topiramate	21 h	First, second, and third trimesters
Ethosuximide	17 to 56 h	Unknown. Assumed window: first, second, and third trimesters
Oxcarbazepine	Oxcarbazepine: immediate-release formulations, about 2 h; extended- release tablet, 7 to 11 h Active metabolite, 10–monohydroxy: 9 to 11 h	Unknown. Assumed window: first, second, and third trimesters
Sulthiame	24 h	Not in TERIS. Assumed window: first, second, and third trimesters
Vigabatrin	10.5 h	Unknown. Assumed window: first, second, and third trimesters
Phenobarbital	70 to 140 h	First, second, and third trimesters
Methylphenobarbital	34 h	Unknown. Assumed window: first, second, and third trimesters
Antifungals		
Fluconazole	30 h	2 weeks before conception and first trimester
Flucytosine	2.4 to 4.8 h	First trimester
Antineoplastics		
Aminopterin	12 to 24 h	First, second, and third trimesters
Asparaginase	5.7 d	3 months before conception and first, second, and third trimesters
Axitinib	2.5 to 6.1 h	1 week before conception and first, second, and third trimesters
Brentuximab vedotin	4 to 6 d	6 months before conception and first, second, and third trimesters
Methotrexate	55 h	6 months before conception and first, second, and third trimesters
Crizotinib	42 h	45 days before conception and first, second, and third trimesters
Cytarabine	1 to 3 h	6 months before conception and first, second, and third trimesters

Drug class/generic name	Half-life	Relevant exposure window ^a
Daunorubicin	The plasma half-life of daunorubicin averages 45 min in the initial phase and 18.5 h in the terminal phase. By 1 h after administration of daunorubicin, the predominant form of the drug in plasma is the metabolite daunorubicinol, which has as average terminal plasma half-life of 26.7 h	6 months before conception and first, second, and third trimesters
Exemestane	24 h	1 month before conception and first, second, and third trimesters
Mechlorethamine	15 min	First, second, and third trimesters
Mercaptopurine	10 h	6 months before conception and first, second, and third trimesters.
Vinblastine	24.8 h	First, second, and third trimesters
Cyclophosphamide	3 to 12 h	12 months before conception and first trimester
Altretamine	4.7 to 10.2 h	Unknown. Assumed window: first, second, and third trimesters
Amsacrine	8 to 9 h	3 months before conception and first, second, and third trimesters
Bevacizumab	480 h	6 months before conception and first, second, and third trimesters
Bleomycin	2 h	Unknown. Assumed window: first, second, and third trimesters
Bortezomib	40 to 193 h	7 months before conception and first, second, and third trimesters
Busulfan	2.3 to 3.4 h	6 months before conception and first, second, and third trimesters
Capecitabine	0.75 h	6 months before conception and first, second, and third trimesters
Carboplatin	2.6 to 5.9 h	Not in TERIS. Assumed window: first, second, and third trimesters
Carmustine	IV, 15 to 75 min	3 months before conception and first, second, and third trimesters
Cetuximab	63 to 230 h	2 months before conception and first, second, and third trimesters
Chlorambucil	1.5 h	Not in TERIS. Assumed window: first, second, and third trimesters
Cisplatin	20 to 30 min	14 months before conception and first, second, and third trimesters

PFIZER CONFIDENTIAL

Drug class/generic name	Half-life	Relevant exposure window ^a
Cladribine	1 d	6 months before conception and first, second, and third trimesters
Clofarabine	5.2 h	6 months before conception and first, second, and third trimesters
Dacarbazine	5 h	Unknown. Assumed window: first, second, and third trimesters
Dactinomycin	36 h	6 months before conception and first, second, and third trimesters
Dasatinib	3 to 5 h	Unknown. Assumed window: first, second, and third trimesters
Docetaxel	11.1 h	6 months before conception and first, second, and third trimesters
Doxorubicin	20 to 48 h	6 months before conception and first, second, and third trimesters
Epirubicin	31.1 h +/- 6 h to 35.3 h +/- 9 h	6 months before conception and first, second, and third trimesters
Erlotinib	36.2 h	2 weeks before conception and first, second, and third trimesters
Estramustine	10 to 20 h	Not in TERIS. Assumed window: first, second, and third trimesters
Etoposide	4 to 11 h	6 months before conception and first, second, and third trimesters
Fludarabine	20 h	6 months before conception and first, second, and third trimesters
Fluorouracil	8 to 20 min	3 months before conception and first, second, and third trimesters
Gemcitabine	1.7 to 19.4 h	6 months before conception and first, second, and third trimesters
Hydroxycarbamide	2 to 4.5 h	Unknown. Assumed window: first, second, and third trimesters
Idarubicin	20 to 22 h	6.5 months before conception and first, second, and third trimesters
Ifosfamide	15 h	Unknown. Assumed window: first, second, and third trimesters
Imatinib	18 h	2 weeks before conception and first, second, and third trimesters
Irinotecan	6 to 12 h	6 months before conception and first, second, and third trimesters
Lapatinib	24 h	1 week before conception and first, second, and third trimesters

PFIZER CONFIDENTIAL

Drug class/generic name	Half-life	Relevant exposure window ^a
Lomustine	16 to 48 h	2 weeks before conception and first, second, and third trimesters
Melphalan	10 to 75 min	Unknown. Assumed window: first, second, and third trimesters
Mitomycin	46 min	6 months before conception and first, second, and third trimesters
Mitoxantrone	23 to 215 h	Not in TERIS. Assumed window: first, second, and third trimesters
Nelarabine	Adults: prodrug: 30 min; ara-G: 3 h	Unknown. Assumed window: first, second, and third trimesters
Oxaliplatin	392 h	9 months before conception and first, second, and third trimesters
Paclitaxel	13 to 52 h	6 months before conception and first, second, and third trimesters
Pemetrexed	3.5 h	6 months before conception and first, second, and third trimesters
Pembrolizumab	22 d	4 months before conception and first, second, and third trimesters
Pentostatin	5.7 h	Not in TERIS. Assumed window: first, second, and third trimesters
Procarbazine	IV, approximately 10 min	Not in TERIS. Assumed window: first, second, and third trimesters
Raltitrexed	260 h	6 months before conception and first, second, and third trimesters
Sorafenib	25 to 48 h	6 months before conception and first, second, and third trimesters
Streptozocin	Systemic: 35 min unchanged drug; 40 h metabolites	1 months before conception and first, second, and third trimesters
Sunitinib	40 to 60 h	1 month before conception and first, second, and third trimesters
Tegafur	6.7 to 11.3 h	6 months before conception and first, second, and third trimesters
Temozolomide	1.8 h	6 months before conception and first, second, and third trimesters
Teniposide	5 h	Not in TERIS. Assumed window: first, second, and third trimesters
Thioguanine	80 min	Not in TERIS. Assumed window: first, second, and third trimesters
Thiotepa	1.4 to 3.7 h	6 months before conception and first, second, and third trimesters

PFIZER CONFIDENTIAL

Drug class/generic name	Half-life	Relevant exposure window ^a
Topotecan	2 to 3 h	6 months before conception and first, second, and third trimesters
Vincristine	85 h	Unknown. Assumed window: first, second, and third trimesters
Vindesine	2.9 h	Not in TERIS. Assumed window: first, second, and third trimesters
Vinorelbine	27.7 to 43.6 h	6 months before conception and first, second, and third trimesters
Lenalidomide	3 h	4 weeks before conception and first, second, and third trimesters
Antithyroid		
Propylthiouracil	1 to 2 h	First and second trimesters
Methimazole	4.9 to 5.7 h	First, second, and third trimesters
Radioiodine	192 h	6-12 months before conception and first, second, and third trimesters
Antivirals		
Ribavirin	12 d	6 months before conception and first, second, and third trimesters
Estrogens		
Diethylstilbestrol	Diethylstilbestrol reaches peak concentration within 20 to 40 min, having a primary half-life of 3 to 6 h. It has a terminal half-life of 2 to 3 d due to entero-hepatic circulation	First, second, and third trimesters
Immunomodulatory agents		
Mycophenolate mofetil	16 h	First, second, and third trimesters
Thalidomide	5 to 7 h	1 month before conception and first, second, and third trimesters
Penicillamine	2 to 4 h	First, second, and third trimesters
Azathioprine	5 h	Primarily first trimester, but other outcomes have been associated with exposures "during pregnancy"
Leflunomide	432 to 456 h	2 years before conception and first, second, and third trimesters
Mycophenolic acid	8 to 16 h	Primarily first trimester, but other outcomes have been associated with exposures "during pregnancy"
Mood stabilizer		
Lithium	24 h	First, second, and third trimesters

PFIZER CONFIDENTIAL

Drug class/generic name	Half-life	Relevant exposure window ^a
NSAIDs		
Indomethacin	4.5 h	Second and third trimesters; unlikely risk associated with first trimester exposure
Prostaglandin analogues		
Misoprostol	20 to 40 min	1 month before conception and first, second, and third trimesters
Retinoids		
Alitretinoin	9 h	1 month before conception and first, second, and third trimesters
Tretinoin	0.5 to 2 h	Unknown. Assumed window: first, second, and third trimesters
Vitamin A	TERIS only notes "long half-life"	Doses above 10,000 IU/day may be teratogenic: First, second, and third trimesters
Acitretin	acitretin: 33 to 96 h cis-acitretin: 28 to 157 h	3 years before conception and throughout pregnancy, especially first trimester
Etretinate	120 d to 3 y	3 years before conception and throughout pregnancy, especially first trimester
Isotretinoin	10 to 12 h	1 month before conception and first, second, and third trimesters
Tazarotene	18 h	First, second, and third trimesters
Retinol	2 to 9 h	12 months before conception and first trimester
Steroids		
Danazol	9.7 to 23.7 h	First, second, and third trimesters
Tetracyclines		
Demeclocycline	10 to 17 h	Second and third trimesters
Oxytetracycline	6 to 11 h	Second and third trimesters
Tetracycline	6 to 11 h	Second and third trimesters; limited data for first trimester exposure
Chlortetracycline	5.6 h	Unknown. Assumed window: second and third trimesters
Doxycycline	18 to 22 h	Unknown. Assumed window: second and third trimesters
Methacycline	14 to 22 h	Unknown. Assumed window: second and third trimesters

Drug class/generic name	Half-life	Relevant exposure window ^a
Minocycline	11 to 24.31 h	Unknown. Assumed window: second and third trimesters
Tigecycline	27 to 43 h	Unknown. Assumed window: second and third trimesters

d = day; h = hour; IV = intravenous; MCM = major congenital malformation; min = minute; NSAIDs = nonsteroidal anti-inflammatory drugs; TERIS = Teratogen Information System; y = year.

Sources: Eltonsy, Martin, Ferreira and Blais ⁷⁷; TERIS ⁷⁸; DrugBank online available at https://go.drugbank.com;

product labels, which are available at: https://www.accessdata.fda.gov/scripts/cder/daf/ and

https://dailymed.nlm.nih.gov/dailymed/index.cfm; summary of product characteristics at https://www.ema.europa.eu/en/medicines and https://products.mhra.gov.uk/; and product monographs at https://www.canada.ca/en/health-canada/services/drugs-health-products/drug-products/drug-products/drug-product-database.html.

^a Teratogens with unknown relevant exposure windows will be assigned an exposure window equivalent to other product(s) in the same class.

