9.3.4. Outcomes

9.3.4.1. Congenital malformations

The study will define and code congenital malformations using the criteria specified by the CDC MACDP and EUROCAT.^{40,41} A malformation may be described and classified by severity (eg, major malformation), by origin (eg, genetic, environmental exposure), and by organ system (eg, urogenital system or malformations known as congenital heart defects [CHD]). An MCM will be defined as any major structural or chromosomal defect detected in live-born infants, stillbirths/fetal losses ≥ 20 gestational weeks, and elective terminations of any gestational age.⁴⁰ This definition is consistent with, but not restricted to, the CDC MACDP and EUROCAT definitions.

To avoid misattribution of the malformation to the medication, MCMs not associated with medication exposure, such as chromosomal abnormalities, genetic syndromes, prematurity-related conditions in infants born at < 36 gestational weeks (eg, patent ductus arteriosus, patent foramen ovale, inguinal hernias, or undescended testes), and positional effects (eg, hip dislocation due to breech position or abnormal skull shape due to crowding by multiple fetuses), will not be considered MCMs in the statistical analyses comparing MCM prevalence between the internal cohorts.⁴² Given that the registry will also use the CDC's MACDP and EUROCAT as external comparators, the registry will include cases of MCMs not associated with medication exposure in the prevalence calculations for this comparison.

Transient malformations in term infants, whether occurring alone or with other malformations, will be reported in the study, as certain transient malformations may be associated with maternal medication exposure in pregnancy and can vary by age of detection and/or age of resolution (eg, CHDs).⁴³ Lastly, the MACDP only includes minor malformations if they occur in the presence of an MCM. However, as stated in the objectives, major and minor malformations are of interest for this study and both will be reported.

Live-born infants with only positional defects (malformations), infectious conditions, or with biochemical abnormalities will be classified and reported separately. The CDC MACDP has different objectives and reporting needs than this project, so a thoughtful adaptation of their guidelines is appropriate.

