Maternal Exposures during Pregnancy

Collected from participants in real time or near real time during pregnancy

- On a weekly basis, exposure to rimegepant or other acute migraine therapies (prescription and nonprescription), including name of product, dates of exposure, and total dose taken on each day of the week, if available
- On a monthly basis, exposure to rimegepant or other preventive migraine therapies (prescription and non-prescription), including name of product, dates of exposure, dose, route, and frequency

Collected from HCP(s)—obstetric and prescriber, if needed

- Exposure to drugs or biological products (including prescription and non-prescription drugs, dietary supplements, vaccines, and known teratogens), including indication/reason for use (for migraine products: acute only, preventive only, or both), dose, route, frequency, and dates/duration of exposure, if available
- Exposure to tobacco, alcohol, marijuana, or recreational or illicit drugs, including timing of exposure, if available

Ongoing pregnancy information

Collected from obstetric HCP; HCPs will only be asked for updates to the data previously reported

- Number of fetuses
- EDD and method of determination
- Prenatal tests performed, including type of test, date of test, and results/findings (eg, congenital malformations)
- Concurrent maternal medical conditions, including but not limited to migraine, diabetes, hypertension, depression
- Concurrent pregnancy-related maternal medical conditions or pregnancy complications

Pregnancy outcome information

Collected from HCP(s)—obstetric and pediatric, if needed

• Pregnancy outcome (SAB, elective termination, TOPFA, live birth, stillbirth)

PFIZER CONFIDENTIAL

- Date of pregnancy outcome
- Gestational age at outcome
- Fetal/infant characteristics, including sex, birth weight, length, head circumference
- Route of delivery
- Delivery/birth complications, if any
- 5-minute Apgar score
- Congenital malformation(s) and potential contributing factors
- For a fetal loss (SAB, stillbirth), factors that may have had an impact on the fetal loss
- For elective termination, reason
- For live birth, prolonged hospitalization after birth

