9.7.3.3. Calculation of outcome prevalence

Prevalence rates of the outcomes of interest will be calculated according to the conventions described in Table 4. In general, the prevalence of each outcome will be calculated by dividing the number of cases of the outcome by the appropriate denominator for that particular outcome, based on clinical knowledge and/or the methodology used by the external comparator. Prevalence is preferred over incidence when examining pregnancy outcomes, such as congenital malformations, because incidence cannot be reliably estimated given the complexities in the reproductive process.⁶⁷

For most outcomes, the main analysis population (denominator) will be the number of pregnant women with pregnancy outcome data, the number of live births, or the number of infants with follow-up data at the timepoint of interest, as appropriate; however, for some outcomes, the main analysis population (denominator) will be restricted based on certain relevant factors:

- For MCM, prevalence in the rimegepant-exposed cohort will be calculated among the subset of women who are exposed during the first trimester.
- For MCM, prevalence will be calculated among live births for the primary analysis, and a secondary analysis will be conducted among live births and fetal losses.
- For preterm birth, SGA, and postnatal growth deficiency, prevalence will be calculated among singleton live births due to the higher risk of these outcomes in twins and higher-order multiples.
- For live birth and infant outcomes (ie, preterm birth, SGA, postnatal growth deficiency, and infant developmental delay), prevalence will be calculated among live births/infants without MCMs.
- For postnatal growth deficiency, infants born preterm or SGA will be excluded from the main analysis population (denominator).
- For infant developmental delay, infants born preterm will be excluded from the main analysis population (denominator).
- For SAB and preterm birth, prevalence will be calculated among the subset of women who are enrolled in the registry prior to 20 and 37 gestational weeks, respectively.
- For some outcomes, prevalence will be calculated at multiple timepoints. For example, postnatal growth deficiency and infant developmental delay will be assessed at 2, 4, 6, and 12 months of

PFIZER CONFIDENTIAL

infant age. At each timepoint, prevalence will be calculated among infants with data available for the particular outcome at that timepoint.

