Secondary analysis: among all pregnancy outcomes with exposure at any time during pregnancy (if applicable for cohort)	Live births and fetal losses with confirmed MCMs (excluding MCMs not associated with medication exposure) among women with pregnancy outcome data and, if applicable, exposure at any time during pregnancy	Live births and fetal losses among women with pregnancy outcome data and, if applicable, exposure at any time during pregnancy	

Table 4.	Calculation of Outcome Prevalence
----------	------------------------------------------

PFIZER CONFIDENTIAL

Outcome	Numerator	Denominator
Comparison with external comparator (CDC MACDP)	Live births and stillbirths with confirmed MCMs (including MCMs not associated with medication exposure) among women with pregnancy outcome data and exposure during the 1 st trimester	Live births among women with pregnancy outcome data and exposure during the 1 st trimester
Comparison with external comparator (Pfizer Study C4951006 [formerly BHVN Outcomes Study])	Live births with confirmed MCMs (excluding MCMs not associated with medication exposure) among women with pregnancy outcome data and exposure at any time during pregnancy	Live births among women with pregnancy outcome data and exposure at any time during pregnancy
Comparison with EUROCAT	Live births and stillbirths and TOPFA with confirmed MCMs (including MCMs not associated with medication exposure) among women with pregnancy outcome data and exposure during the 1 st trimester	Live births and stillbirths among women with pregnancy outcome data and exposure during the 1 st trimester
Secondary Outcomes		
Minor congenital malformations	Live births with minor congenital malformations among women with pregnancy outcome data	Live births among women with pregnancy outcome data
Gestational diabetes		
Primary analysis between internal cohorts	Gestational diabetes among women with pregnancy outcome data	Women with pregnancy outcome data
Comparison with external comparator (CDC NVSS)	Gestational diabetes among live births	Live births among women with pregnancy outcome data
Gestational hypertension		
Primary analysis between internal cohorts	Gestational hypertension among women with pregnancy outcome data	Women with pregnancy outcome data
Comparison with external comparator ⁶¹	Gestational hypertension among live births	Live births among women with pregnancy outcome data
Pre-eclampsia		

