9.7.3.7. Sensitivity analyses

Sensitivity analyses will also be conducted to examine the extent to which changes in certain methods or assumptions affect the results. The following sensitivity analyses are planned:

• For the primary outcome, MCM, a sensitivity analysis will be conducted that excludes women exposed to known teratogens (eg, valproic acid and topiramate) from the main analysis population. Participants will be considered exposed during pregnancy if a dose is taken at any time during pregnancy (from conception to pregnancy outcome) or prior to conception (up to 5 product half-lives prior to conception). A list of teratogens has been developed (ANNEX 4) and will be continually updated based on the data available in the Teratogen Information System (TERIS) database of teratogenic agents and recent publications.⁷²⁻⁷⁴

PFIZER CONFIDENTIAL

- A sensitivity analysis will be conducted that applies a stricter definition of prospective enrollment. For this analysis, women who enroll in the registry prior to diagnostic prenatal testing will be considered prospectively enrolled, and women who enroll in the registry after diagnostic prenatal testing, regardless of the results, will be considered retrospectively enrolled. The outcomes of women who enroll prior to diagnostic prenatal testing will be compared with those of women who enrolled after diagnostic prenatal testing.
- For the primary outcome, MCM, a sensitivity analysis will be conducted that includes congenital malformations that are chromosomal or genetic.

Separate sensitivity analyses may also be conducted to assess the potential impact of missing data.

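### The MCM teratogen sensitivity analysis counts misoprostol given to induce labour or carry out a termination as teratogen exposure, so it removes women because of how the pregnancy ended

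*Protocol*

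**What the plan says.** Section 9.7.3.7 plans, for MCM, that "a sensitivity analysis will be conducted that excludes women exposed to known teratogens (eg, valproic acid and topiramate) from the main analysis population". Exposure for this purpose means that "a dose is taken at any time during pregnancy (from conception to pregnancy outcome) or prior to conception", the last part limited to 5 product half-lives. The rule does not ask why the drug was given.

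The list of teratogens is Annex 4, Table 7. Its misoprostol row, under prostaglandin analogues, has the window "1 month before conception and first, second, and third trimesters". Other rows of the table carry the same words; the point here is the misoprostol row. It has no note on reason for use.

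Three other places matter:

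- **Data capture.** At follow-up, including at the pregnancy outcome, the healthcare provider reports "Exposure to drugs or biological products (including prescription and non-prescription drugs, dietary supplements, vaccines, and known teratogens" with reason for use and dates (section 9.4.1.2). A dose given near the end of pregnancy can therefore reach the dataset.
- **MCM definition.** Section 9.3.4.1 counts defects in live births, in stillbirths and losses from 20 weeks, and in "elective terminations of any gestational age".
- **Denominators.** Section 9.7.3.3 says for MCM that "prevalence will be calculated among live births for the primary analysis, and a secondary analysis will be conducted among live births and fetal losses". In Table 4 the numerator of the wider rows is "Live births and fetal losses with confirmed MCMs (excluding MCMs not associated with medication exposure").

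**The concern.** The sensitivity analysis exists to remove women whose infant's malformation might be due to another drug. A dose given to induce labour, or to end a pregnancy after an anomaly has been diagnosed, comes after the malformation and cannot have caused it. Under the written rule such a dose still counts. Using the Annex 4 window in place of the 5-half-life rule would not help, because the misoprostol window itself covers all three trimesters.

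Elsewhere the protocol does take timing into account. Section 9.7.3.3 restricts rimegepant exposure to the first trimester for MCM. Section 9.4.4 has each malformation assessed for its temporal relation to exposure. The sulfamethoxazole/trimethoprim row of Annex 4 gives different windows for different outcomes.

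Two things are at stake. Among live births, women are lost for an irrelevant exposure. In any version of the analysis that includes fetal losses, a termination for fetal anomaly carried out with misoprostol would be deleted because of the termination itself, so selection would depend on the outcome. Section 9.9 presents this analysis as the answer to teratogen use in the comparison cohort, so it should not bring in a selection problem of its own.

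**Working it through.** The protocol does not mention obstetric uses of misoprostol or their frequency. Those uses are general clinical knowledge, and every usage share below is an assumption.

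**1. The protocol's power figures (section 9.5.2, Table 2).** Inputs: reference rate 3%, two-sided α = 0.05, equal cohorts, normal approximation. With p̄ the mean of the two rates,

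power = Φ{ [ (p₂ − p₁)√n − 1.96·√(2p̄(1 − p̄)) ] / √[ p₁(1 − p₁) + p₂(1 − p₂) ] }.

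- n = 390, 3% v 7.5% (relative risk 2.5): 80.6%. The protocol states 80.6%.
- Evaluable number: 390 × 0.90 × 0.90 = 315.9, or 316.
- n = 316, 3% v 8.1% (relative risk 2.7): 80.1%. The protocol states 80%.

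**2. Live births: loss of precision.** Let a share f of each cohort's 316 be removed, unrelated to MCM and to cohort.

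| f (assumed) | n per cohort | Power at relative risk 2.7 | Relative risk detectable with 80% power |
|---|---|---|---|
| 0 | 316 | 80.1% | 2.70 |
| 5% | 300 | 78.0% | 2.75 |
| 10% | 284 | 75.8% | 2.82 |
| 20% | 253 | 70.8% | 2.96 |

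These figures only set the scale. The protocol promises no power for this sensitivity analysis.

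**3. Rows with fetal losses: cases at risk of deletion.** Inputs: 3% MCM; TOPFA rate 0.4% (Table 3); 10% lost to follow-up (section 9.5.2).

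- Women followed per cohort: 390 × 0.90 = 351.
- Expected live-born cases: L = 0.03 × 316 = 9.48.
- Expected TOPFA, all treated as eligible MCM: T = 0.004 × 351 = 1.40.
- Total: 10.88.
- All TOPFA deleted: 1.40 / 10.88 = 13%. Half deleted: 0.70 / 10.88 = 6%.

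This is an upper bound. TOPFA covers any fetal anomaly, while these rows leave out chromosomal and genetic cases. If half of TOPFA were of that kind (assumed), T = 0.70 and the total is 10.18. Deleting half to all of them then removes 0.35 / 10.18 = 3% to 0.70 / 10.18 = 7%.

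**4. When the relative risk moves.** Let r_L and r_T be the true relative risks for live-born and TOPFA cases, and m_E and m_C the shares of TOPFA deleted in the exposed and comparison cohorts. Ignoring the small change in denominators,

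RR = [ L·r_L + T(1 − m_E)·r_T ] / [ L + T(1 − m_C) ].

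- If r_L = r_T = r and m_E = m_C, then RR = r: no shift.
- If r_L = 1.5 and r_T = 4 (chosen), the value before deletion is (14.22 + 5.62) / 10.88 = 1.82. It becomes (14.22 + 2.81) / 10.18 = 1.67 with half deleted in both cohorts, and 14.22 / 9.48 = 1.50 with all deleted.
- If r_L = r_T = 1, with all TOPFA deleted in the exposed cohort and half in the comparison cohort (chosen), RR = 9.48 / 10.18 = 0.93. With the shares reversed, RR = 10.18 / 9.48 = 1.07.

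**The case against.** The strongest reply is that little depends on this. One sensitivity analysis is affected, and the primary MCM analysis keeps all these women. How often such doses would be reported is unknown. Section 9.7.3.7 ties the exclusion to the primary outcome, whose primary analysis is among live births and so contains no TOPFA. Nothing says that the exclusion is repeated on the fetal-loss rows, although Table 4 lists those rows under the primary outcome. All of this stands and limits the point, but it does not remove the defect in the rule.

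A reader might infer more than the protocol supports:

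- **That the study's power target is missed.** The 80% refers to the full cohorts, not to this analysis.
- **That managing a miscarriage deletes malformation cases.** A spontaneous abortion is a loss before 20 weeks, and section 9.3.4.1 counts spontaneous losses only from 20 weeks, so no MCM case is deleted. Section 9.3.4.2 also lets fetal death itself mark a spontaneous abortion or stillbirth. A later dose may then fall after the outcome and outside the window. The text does not settle this.
- **That TOPFA are removed because they are cases.** The trigger is the drug, so terminations without an anomaly would be removed as well.
- **That the relative risk is biased from 1.82 towards 1.50.** The arithmetic is right, but it follows from the chosen 1.5-fold and 4-fold effects. With equal effects and equal misoprostol use there is no shift.

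**Conclusion.** The point holds in a limited form. Read literally, section 9.7.3.7 and the misoprostol row remove women from the MCM teratogen sensitivity analysis for doses that result from how the pregnancy ended.

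Among live births the cost is mainly precision: about 300 to 253 per cohort in place of 316, if 5% to 20% are affected. Only if the exclusion is also applied to the Table 4 rows with fetal losses can cases be deleted. The bound is then about 6% to 13% of expected cases if half to all TOPFA used misoprostol, and lower once chromosomal and genetic cases are left out. The relative risk shifts only if the TOPFA share or misoprostol use differs between cohorts.

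The actual size cannot be derived from the protocol. This is a clarification worth considering, not a threat to the main result.

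**What to change.** Edit both places, since the operative rule is in section 9.7.3.7 and the window is in Annex 4.

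- State in section 9.7.3.7, and in a note to the misoprostol row, that for the MCM sensitivity analysis a dose given as part of the delivery, termination or loss management that actually ended the pregnancy does not count as teratogen exposure.
- State that any earlier dose still counts, including a failed termination attempt after which the pregnancy continued. A blanket exemption by reason for use would wrongly keep such a woman. No trimester cut-off is needed.
- Apply the same rule to any other Annex 4 agent given to bring about the pregnancy outcome.

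This changes how a recorded dose is classified for analysis and nothing in clinical care. It costs a sentence or two and a table note. Dates, reason for use, date of outcome and reason for elective termination are already collected. A few records without a reason for use will need a query. Comparative analyses are run only at the end (section 9.7) and data collection is planned to April 2034 (section 6), so the change can be made before any comparison is seen.
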